Clinical Trial Protocol

Document Number:		c24401085-02
EudraCT No.	2018-002792-18	
BI Trial No.	1405-0007	
BI Investigational Medicinal Product	BI 1323495	
Title	Relative bioavailability of BI 1323495 following oral administration under fed and fasted conditions in healthy male subjects (an open-label, randomised, single-dose, two-period, two-sequence crossover study)	
Lay Title	A study to test how food influences the amount of BI 1323495 in the blood of healthy men	
Clinical Phase	I	
Trial Clinical Monitor	
Phone: Fax:
	
Principal Investigator	
Phone: Fax:
	
Status	Final Protocol (Revised Protocol (based on global amendment 1))	
Version and Date	Version: 2.0	Date: 22 November 2018
Page 1 of 61		

Proprietary confidential information © 2018 Boehringer Ingelheim International GmbH or one or more of its affiliated companies. All rights reserved. This document may not - in full or in part - be passed on, reproduced, published or otherwise used without prior written permission
		

CLINICAL TRIAL PROTOCOL SYNOPSIS

Company name	Boehringer Ingelheim
Protocol date	1 August 2018
Revision date	22 November 2018
BI trial number	1405-0007
Title of trial	Relative bioavailability of BI 1323495 following oral administration under fed and fasted conditions in healthy male subjects (an open-label, randomised, single-dose, two-period, two-sequence crossover study)
Principal Investigator	
Trial site	
Clinical phase	I
Trial rationale	This food interaction study will generate pharmacokinetic information under fed conditions versus the fasted state to support the future development in patients.
Trial objective	To investigate the relative bioavailability of a single oral dose of BI 1323495 under fed and fasted conditions
Trial design	Randomised, open-label, two-way crossover design
Trial endpoints	Primary endpoints: AUC_{0-tz} and C_{max} of BI 1323495 Secondary endpoints: $AUC_{0-\infty}$ of BI 1323495
Number of subjects	
total entered	12
each treatment	12
Diagnosis	Not applicable
Main criteria for inclusion	Healthy male subjects, age of 18 to 45 years (inclusive), body mass index (BMI) of 18.5 to 29.9 kg/m ² (inclusive)
Test product	BI 1323495 tablet formulation
dose	
mode of admin.	Oral with 240 mL of water following a high fat, high calorie meal (treatment test (T)) and after an overnight fast of at least 10 h (treatment reference (R))

Proprietary confidential information © 2018 Boehringer Ingelheim International GmbH or one or more of its affiliated companies

Duration of treatment	One day (single dose) for each treatment
Statistical methods	
Relative bioavailability will be estimated by the ratios of the geometric means (test/reference) for the primary and secondary endpoints. Additionally, their two-sided 90% confidence intervals (CIs) will be provided. This method corresponds to the two one-sided t-test procedure, each at a 5% significance level. Since the main focus is on estimation and not testing, a formal hypothesis test and associated acceptance range is not specified. The statistical model will be an analysis of variance (ANOVA) on the logarithmic scale including effects for sequence, subjects nested within sequences, period and treatment. CIs will be calculated based on the residual error from the ANOVA.
 
Descriptive statistics will be calculated for all endpoints.

FLOW CHART

TABLE OF CONTENTS

TITLE PAGE	1
CLINICAL TRIAL PROTOCOL SYNOPSIS	2
FLOW CHART	4
TABLE OF CONTENTS	5
ABBREVIATIONS	9
1. INTRODUCTION.....	11
1.1 MEDICAL BACKGROUND.....	11
1.2.4 Clinical experience in humans	14
1.2.4.1 Clinical experience with BI 1323495	14
1.2.5 Residual Effect Period	19
1.3 RATIONALE FOR PERFORMING THE TRIAL	19
1.4 BENEFIT - RISK ASSESSMENT	19
2. TRIAL OBJECTIVES AND ENDPOINTS.....	22
2.1 MAIN OBJECTIVES, PRIMARY AND SECONDARY ENDPOINTS	22
2.1.1 Main objectives.....	22
2.1.2 Primary endpoints	22
2.1.3 Secondary endpoint	22
3. DESCRIPTION OF DESIGN AND TRIAL POPULATION.....	24
3.1 OVERALL TRIAL DESIGN AND PLAN	24
3.2 DISCUSSION OF TRIAL DESIGN, INCLUDING THE CHOICE OF CONTROL GROUPS.....	24
3.3 SELECTION OF TRIAL POPULATION	24
3.3.1 Main diagnosis for trial entry	24
3.3.2 Inclusion criteria	24
3.3.3 Exclusion criteria	25
3.3.4 Withdrawal of subjects from treatment or assessments	26
3.3.4.1 Discontinuation of trial treatment	27

Proprietary confidential information © 2018 Boehringer Ingelheim International GmbH or one or more of its affiliated companies

3.3.4.2 Withdrawal of consent to trial participation	27
3.3.4.3 Discontinuation of the trial by the sponsor	27
3.3.5 Replacement of subjects	28
4. TREATMENTS.....	29
4.1 INVESTIGATIONAL TREATMENTS	29
4.1.1 Identity of the Investigational Medicinal Products	29
4.1.2 Selection of doses in the trial and dose modifications.....	29
4.1.3 Method of assigning subjects to treatment groups	30

8.2	DATA QUALITY ASSURANCE	52
8.3	RECORDS	52
8.3.1	Source documents	52
8.3.2	Direct access to source data and documents.....	53
8.3.3	Storage period of records	53
8.4	EXPEDITED REPORTING OF ADVERSE EVENTS	54
8.5	STATEMENT OF CONFIDENTIALITY AND SUBJECT PRIVACY.....	54

8.5.1	Collection, storage and future use of biological samples and corresponding data	54
8.6	TRIAL MILESTONES	54
8.7	ADMINISTRATIVE STRUCTURE OF THE TRIAL	55
9.	REFERENCES	56
9.1	PUBLISHED REFERENCES.....	56
9.2	UNPUBLISHED REFERENCES.....	58
10.	APPENDICES	59
11.	DESCRIPTION OF GLOBAL AMENDMENT(S)	60
	11.1 GLOBAL AMENDMENT 1	60

ABBREVIATIONS

ADME	Absorption, distribution, metabolism, and excretion
AE	Adverse event
AESI	Adverse events of special interest
ANOVA	Analysis of variance
AUC _{0-∞}	Area under the concentration-time curve of the analyte in plasma over the time interval from 0 extrapolated to infinity
AUC _{0-tz}	Area under the concentration-time curve of the analyte in plasma over the time interval from 0 to the last quantifiable data point
BI	Boehringer Ingelheim
BMI	Body mass index (weight divided by height squared)
BP	Blood pressure
CA	Competent authority
CI	Confidence interval
C _{max}	Maximum measured concentration of the analyte in plasma
CML	Clinical Monitor Local
CRF	Case Report Form, paper or electronic (sometimes referred to as 'eCRF')
CTP	Clinical trial protocol
CTR	Clinical trial report
DILI	Drug induced liver injury
ECG	Electrocardiogram
eCRF	Electronic case report form
eDC	Electronic data capture
EDTA	Ethylenediaminetetraacetic acid
EoTrial	End of trial
EudraCT	European Clinical Trials Database
FU	Follow-up
GCP	Good Clinical Practice

HR	Heart rate
IB	Investigator's brochure
IC ₅₀	Half-maximal inhibitory concentration
IEC	Independent Ethics Committee
IPV	Important protocol violation
IRB	Institutional Review Board
ISF	Investigator site file
LC-MS/MS	Liquid chromatography with tandem mass spectrometry
MDA	Methylenedioxymethamphetamine
MDMA	Methylenedioxymethamphetamine
MedDRA	Medical Dictionary for Regulatory Activities
NOAEL	No observed adverse effect level
PK	Pharmacokinetic(s)
PKS	Pharmacokinetic set
PR	Pulse rate
QT	Time between start of the Q-wave and the end of the T-wave in an electrocardiogram
QTc	QT interval corrected for heart rate using the method of Fridericia (QTcF) or Bazett (QTcB)
R	Reference treatment
REP	Residual effect period
SAE	Serious adverse event
SCR	Screening
SOP	Standard operating procedure
T	Test product or treatment
TS	Treated set
TSAP	Trial statistical analysis plan
ULN	Upper limit of normal
XTC	Ecstasy

1. INTRODUCTION

This trial will investigate the effect of food on pharmacokinetics of BI 1323495.

1.1 MEDICAL BACKGROUND

1.2 DRUG PROFILE

For a more detailed description of the BI 1323495 profile, please refer to the current Investigator's Brochure (IB) ([c21238478-01](#)).

1.2.4 Clinical experience in humans

1.2.4.1 Clinical experience with BI 1323495

At the time of CTA submission of this trial, the first in man study 1405-0001 had been initiated. This partially randomized within dose groups, placebo-controlled trial investigates the safety, tolerability, pharmacokinetics and pharmacodynamics of single rising oral doses of BI 1323495 as tablet formulation. As of 14 November 2018, the clinical part has been completed as planned. A total of 63 subjects were randomized to treatment with either

Proprietary confidential information © 2018 Boehringer Ingelheim International GmbH or one or more of its affiliated companies

placebo (N=15) or single ascending doses of

BI 1323495 (N=6 per dose). An overview on preliminary results of this trial is given in the following.

Treatments with BI 1323495 tablets or placebo were safe and well tolerated at all doses investigated. Overall, 16 out of 48 subjects treated with BI 1323495 (33.3%) and 2 out of 15 subjects treated with placebo (13.3%) were reported with at least 1 AE following drug administration. No dose dependency was observed for the different BI 1323495 treatment groups. The most frequently reported AE was headache, observed in 6 subjects (12.5%) dosed with BI 1323495 and 2 subjects (13.3%) on placebo. The incidence of headache appeared similar between the different BI 1323495 dose groups and placebo.

AEs were generally of short duration and mild in intensity apart from 1 case of moderate headache
moderate common cold reported by
one subject
, and 1 case of moderate rhinitis

. Severe or serious AEs were not reported. All AEs were followed-up until resolved.

A summary of AEs reported following study drug treatment is shown in Table [1.2.4.1: 1](#).

Table 1.2.4.1: 1 Number (percentage) of subjects with AEs following administration of BI 1323495 or placebo in SRD trial 1405-0001

AE reported term	Placebo	BI 1323495									
										Total BI	
		N (%)	N (%)	N (%)	N (%)	N (%)	N (%)	N (%)	N (%)	N (%)	N (%)
No. of subjects	15 (100.0)	6 (100.0)	6 (100.0)	6 (100.0)	6 (100.0)	6 (100.0)	6 (100.0)	6 (100.0)	6 (100.0)	48 (100.0)	
Total with on treatment AEs	2 (13.3)	3 (50.0)	2 (33.3)	1 (16.7)	2 (33.3)	1 (16.7)	2 (33.3)	3 (50.0)	2 (33.3)	16 (33.3)	
Headache	2 (13.3)	3 (50.0)	1 (16.7)	-	-	-	-	1 (16.7)	1 (16.7)	6 (12.5)	
Tiredness	-	-	-	1 (16.7)	1 (16.7)	-	-	-	-	2 (4.2)	
Diarrhoea	-	-	1 (16.7)	-	-	-	-	1 (16.7)	-	2 (4.2)	
Stiff neck	-	-	-	-	1 (16.7)	-	-	-	-	1 (2.1)	

1.2.5 Residual Effect Period

The Residual Effect Period (REP) of BI 1323495, i.e., the time interval when measurable drug levels or PD effects are still likely to be present after administration, is not yet known. Therefore, all AEs with an onset between start of treatment and the end of trial examination (last per protocol contact) will be considered on treatment.

1.3 RATIONALE FOR PERFORMING THE TRIAL

In the ongoing single rising dose study, only pharmacokinetic data under fasted conditions are investigated for BI 1323495. The planned food interaction study will generate pharmacokinetic information under fed conditions to support the future development in patients.

1.4 BENEFIT - RISK ASSESSMENT

Participation in this clinical trial is without any (therapeutic) benefit for healthy subjects. Their participation, however, is of major importance for the development of a new orally available drug, which might improve the therapy in patients with COPD and emphysema. The subjects are exposed to the risks of the study procedures and the risks related to the exposure to the trial medication.

Procedure-related risks

The use of an indwelling venous catheter or venepuncture for e.g. blood sampling may result in mild bruising, and in rare cases, in transient inflammation of the wall of the vein, or nerve injury, potentially resulting in paraesthesia, reduced sensibility, and/or pain for an indefinite period.

The total volume of blood withdrawn per subject during the entire study will not exceed the volume of a normal blood donation (500 mL). No health-related risk to healthy subjects is expected from withdrawal of this volume of blood.

Drug-related risks and safety measures

In this food effect trial, subjects will receive two single doses of _____ once under fasted and once under fed conditions. Administration of BI 1323495 under fed conditions may cause an increase of plasma concentrations of BI 1323495. However, based on modelling data for the tablet formulation used in the SRD trial and this food effect trial only a minimal food effect is expected for a dose of _____ resulting in plasma concentrations below those exposures seen in the SRD trial following doses of _____ and above.

2. TRIAL OBJECTIVES AND ENDPOINTS

2.1 MAIN OBJECTIVES, PRIMARY AND SECONDARY ENDPOINTS

2.1.1 Main objectives

The main objective of this trial is to assess the effect of food on the pharmacokinetics of an oral tablet formulation [REDACTED] of BI 1323495 by investigating the relative bioavailability following single dose administration under fed and fasted conditions.

2.1.2 Primary endpoints

The following pharmacokinetic parameters will be determined for BI 1323495:

- AUC_{0-tz} (area under the concentration-time curve of the analyte in plasma over the time interval from 0 to the last quantifiable data point)
- C_{max} (maximum measured concentration of the analyte in plasma)

2.1.3 Secondary endpoint

The following pharmacokinetic parameter will be determined for BI 1323495:

- $AUC_{0-\infty}$ (area under the concentration-time curve of the analyte in plasma over the time interval from 0 extrapolated to infinity)

3. DESCRIPTION OF DESIGN AND TRIAL POPULATION

3.1 OVERALL TRIAL DESIGN AND PLAN

The study will be performed as a randomised, open-label, two-way crossover trial in healthy male subjects in order to compare the test treatment (T) to the reference treatment (R). The treatments will be two single oral doses of BI 1323495 separated by a washout period between the treatments:

Treatment T: tablets of BI 1323495, fed

Treatment R: tablets of BI 1323495, fasted

The subjects will be randomly allocated to the 2 treatment sequences (T-R or R-T). For details, refer to Section [4.1](#).

An overview of all relevant trial activities is provided in the [Flow Chart](#). For visit schedule and details of trial procedures at selected visits, refer to Sections [6.1](#) and [6.2](#), respectively.

3.2 DISCUSSION OF TRIAL DESIGN, INCLUDING THE CHOICE OF CONTROL GROUPS

For relative bioavailability trials, the crossover design is preferred because of its efficiency: since each subject serves as his own control, the comparison between treatments is based on an intra-subject comparison, thus removing inter-subject variability from the comparison between treatments ([R94-1529](#)).

The open-label treatment is not expected to bias results, since the study endpoints are derived from measurement of plasma concentrations of the analyte, which are provided by a bioanalytical laboratory that is blinded to treatment allocation.

3.3 SELECTION OF TRIAL POPULATION

It is planned that 12 healthy male subjects will enter the study. They will be recruited from the volunteers' pool of the trial site.

Only male subjects will be included in the study because no data on reproductive toxicology are available at this time.

A log of all subjects enrolled into the trial (i.e. who have signed informed consent) will be maintained in the ISF irrespective of whether they have been treated with investigational drug or not.

3.3.1 Main diagnosis for trial entry

The study will be performed in healthy subjects.

3.3.2 Inclusion criteria

Subjects will only be included in the trial if they meet the following criteria:

Proprietary confidential information © 2018 Boehringer Ingelheim International GmbH or one or more of its affiliated companies

1. Healthy male subjects according to the assessment of the investigator, as based on a complete medical history including a physical examination, vital signs (BP, PR), 12-lead ECG, and clinical laboratory tests
2. Age of 18 to 45 years (inclusive)
3. BMI of 18.5 to 29.9 kg/m² (inclusive)
4. Signed and dated written informed consent prior to admission to the study, in accordance with GCP and local legislation

3.3.3 Exclusion criteria

Subjects will not be allowed to participate, if any of the following general criteria apply:

1. Any finding in the medical examination (including BP, PR or ECG) deviating from normal and assessed as clinically relevant by the investigator
2. Repeated measurement of systolic blood pressure outside the range of 90 to 140 mmHg, diastolic blood pressure outside the range of 50 to 90 mmHg, or pulse rate outside the range of 50 to 90 bpm
3. Any laboratory value outside the reference range that the investigator considers to be of clinical relevance
4. Any evidence of a concomitant disease assessed as clinically relevant by the investigator
5. Gastrointestinal, hepatic, renal, respiratory, cardiovascular, metabolic, immunological or hormonal disorders
6. Cholecystectomy or other surgery of the gastrointestinal tract that could interfere with the pharmacokinetics of the trial medication (except appendectomy or simple hernia repair)
7. Diseases of the central nervous system (including but not limited to any kind of seizures or stroke), and other relevant neurological or psychiatric disorders
8. History of relevant orthostatic hypotension, fainting spells, or blackouts
9. Chronic or relevant acute infections
10. History of relevant allergy or hypersensitivity (including allergy to the trial medication or its excipients)
11. Use of drugs within 30 days of planned administration of trial medication that might reasonably influence the results of the trial (including drugs that cause QT/QTc interval prolongation)
12. Intake of an investigational drug in another clinical trial within 60 days of planned administration of investigational drug in the current trial, or concurrent participation in another clinical trial in which investigational drug is administered
13. Smoker (more than 10 cigarettes or 3 cigars or 3 pipes per day)
14. Inability to refrain from smoking on specified trial days
15. Alcohol abuse (consumption of more than 30 g per day)
16. Drug abuse or positive drug screening
17. Blood donation of more than 100 mL within 30 days of planned administration of trial medication or intended blood donation during the trial

Proprietary confidential information © 2018 Boehringer Ingelheim International GmbH or one or more of its affiliated companies

18. Intention to perform excessive physical activities within one week prior to the administration of trial medication or during the trial
19. Inability to comply with the dietary regimen of the trial site
20. A marked baseline prolongation of QT/QTc interval (such as QTc intervals that are greater than 450 ms, if confirmed by a 2nd ECG recording) or any other relevant ECG finding at screening
21. A history of additional risk factors for *Torsade de Pointes* (such as heart failure, hypokalaemia, or family history of Long QT Syndrome)
22. Subject is assessed as unsuitable for inclusion by the investigator, for instance, because the subject is not considered able to understand and comply with study requirements, or has a condition that would not allow safe participation in the study

23. Subjects with female partner of childbearing potential who are unwilling to use male contraception (condom or sexual abstinence) from the first administration of trial medication until 30 days after last administration of trial
24. Current or history of relevant kidney, urinary tract diseases or abnormalities (e.g. nephrolithiasis, hydronephrosis, acute or chronic nephritis, renal injury, renal failure)
25. Estimated glomerular filtration rate according to CKD-EPI formula < 90 mL/min at screening
26. Within 10 days prior to administration of trial medication, use of any drug that could reasonably inhibit platelet aggregation or coagulation (e.g., acetylsalicylic acid)
27. Liver enzyme (ALT, AST, GGT) values above upper limit of normal at the screening examination

For study restrictions, refer to Section [4.2.2](#).

3.3.4 Withdrawal of subjects from treatment or assessments

Subjects may discontinue trial treatment or withdraw consent to trial participation as a whole ('withdrawal of consent') with very different implications; please see Sections [3.3.4.1](#) and [3.3.4.2](#) below.

If a subject is removed from or withdraws from the trial prior to the first administration of trial medication, the data of this subject will not be entered in the case report form (CRF) and will not be reported in the clinical trial report (CTR). If a subject is removed from or withdraws from the trial after the first administration of trial medication, this will be documented and the reason for discontinuation must be recorded in the CRF; in addition, the data will be included in the CRF and will be reported in the CTR. At the time of discontinuation, a complete end of trial examination will be performed, if possible, and the information will be recorded in the CRF. If the discontinuation occurs before the end of the REP (see Section [1.2.5](#)), the discontinued subject should if possible be questioned for AEs and concomitant therapies at or after the end of the REP in order to ensure collection of AEs and concomitant therapies throughout the REP, if not contrary to any consent withdrawal of the subject.

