7.3.4 Safety analyses

Safety will be analysed based on the assessments described in Section [2.2.2.2](#). All treated subjects (TS, refer to Section [7.3](#)) will be included in the safety analysis. Safety analyses will be descriptive in nature and based on BI standards. No hypothesis testing is planned.

For all analyses, the treatment actually administered (= treatment at onset) to the subject will be used (any deviations from the randomised treatment will be discussed in the minutes of the Report Planning Meeting).

Treatments will be compared in a descriptive way. Tabulations of frequencies/proportions will be used to evaluate categorical (qualitative) data, and tabulations of descriptive statistics will be used to analyse continuous (quantitative) data.

Measurements (such as ECG, vital signs, or laboratory parameters) or AEs will be assigned to treatments (see Section [4.1](#)) based on the actual treatment at the planned time of the measurement or on the recorded time of AE onset (concept of treatment emergent AEs). Therefore, measurements planned or AEs recorded prior to first intake of trial medication will be assigned to the screening period, those between first trial medication intake and end of trial termination date will be assigned to the treatment period. These assignments including the corresponding time intervals will be defined in detail in the TSAP. Note that AEs occurring after the last per protocol contact but entered before final database lock will be reported to Pharmacovigilance only and will not be captured in the trial database.

Additionally, further treatment intervals (analysing treatments) may be defined in the TSAP in order to provide summary statistics for time intervals, such as combined treatments, on-treatment totals, or periods without treatment effects (such as screening and follow-up intervals).

Adverse events will be coded using the Medical Dictionary for Regulatory Activities (MedDRA). Frequency, severity, and causal relationship of AEs will be tabulated by treatment, system organ class, and preferred term. SAEs, AESIs (see Section [5.2.5.1](#)), and other significant AEs (according to ICH E3) will be listed separately.

Previous and concomitant therapies will be presented per treatment group without consideration of time intervals and treatment periods.

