6.7 BASELINE, TIME WINDOWS AND CALCULATED VISITS

For vital signs baseline for Period 1 is defined as the last measurement prior to first drug administration, and baseline for Period 2 is defined as the last measurement prior to first drug administration in Period 2.

For laboratory parameters baseline for Period 1 and Period 2 is defined as the last measurement prior to first drug administration, as the REP of BI 1323495 is not known.

Section 6.1 of the CTP: *Exact times of measurements outside the permitted time windows will be documented. The acceptable time windows for screening, for measurements and assessments scheduled to occur 'before' trial medication administration on Day 1, and the end of trial examination are provided in the Flow Chart.*

The acceptable deviation from the scheduled time for vital signs, ECG and laboratory tests will be ± 15 min for the first 4 h after trial drug administration and ± 30 min thereafter. Starting from 48 h post administration a deviation from the scheduled time for vital signs, ECG and laboratory tests of ± 120 min is acceptable.

If scheduled in the Flow Chart at the same time as a meal, blood sampling, vital signs, and 12-lead ECG recordings have to be done first. Furthermore, if several measurements including venepuncture are scheduled for the same time, venepuncture should be the last of the measurements due to its inconvenience to the subject and possible influence on physiological parameters.

Adherence to time windows will be checked via the consistency check listings at the RPM/DBLM.

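### Does tying AE questioning of discontinued subjects to an unknown residual effect period leave a safety gap that needs repair?

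*Protocol*

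**What the plan says.** Protocol Section 3.3.4 deals with subjects removed or withdrawing after the first dose. It says: "At the time of discontinuation, a complete end of trial examination will be performed, if possible". It then adds a condition on the residual effect period (REP): "If the discontinuation occurs before the end of the REP", the subject "should if possible be questioned for AEs and concomitant therapies at or after the end of the REP", unless his withdrawal of consent rules this out. The section refers to 1.2.5 for the REP.

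Section 1.2.5 gives no figure. The span over which drug or effects "are still likely to be present after administration, is not yet known". The substitute rule is that "all AEs with an onset between start of treatment and the end of trial examination (last per protocol contact) will be considered on treatment". The SAP takes the same position: Section 6.7 sets the laboratory baseline as it does "as the REP of BI 1323495 is not known", and Section 6.1 defines no follow-up phase.

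Protocol Section 7.3.4 adds that "AEs occurring after the last per protocol contact but entered before final database lock will be reported to Pharmacovigilance only". Section 5.1.5.2.1 ends active collection in the CRF at the individual subject's end of trial.

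Section 3.3.4.1 treats stopping of treatment separately. Such a subject stays in the trial if he agrees, and is followed as set out in the Flow Chart and Section 6.2.3.

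**The concern.** The instruction depends on a date that the protocol says it does not have. A site cannot work out from the text whether a subject has left before the REP is over, or when the questioning falls due.

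The substitute rule seems to make this worse. It runs to the end of trial examination, which for someone leaving the trial takes place when he leaves. Since Section 1.2.5 treats that examination as the last per-protocol contact, an AE first reported afterwards might be kept out of the trial database under Section 7.3.4.

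At stake is the completeness of the AE tables. Subjects who leave early may do so because of AEs, and Section 3.3.5 does not replace those withdrawn for drug-related events. If their observation is cut short, late events would be under-counted where they may be most likely.

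**Working it through.** The plan states no figure for the REP or for AE follow-up after discontinuation, so there is nothing to reproduce. The check is a reading of the linked rules, plus day counts.

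**Can the instruction be followed?** With an unknown REP, a site can treat any early exit as falling before its end. The questioning is due at or after that end, with no upper limit, so a late contact complies. Section 3.3.4 also gives the purpose: to collect AEs and concomitant therapies over the whole REP. The due date is missing; the intention is not.

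**Does the window close on the day of stopping?** It depends on how the subject stops.
- *Leaves the trial.* Section 3.3.4 puts the examination at that time, so the literal reading is possible. Where consent is withdrawn, further contact may be barred whatever the protocol says.
- *Stops treatment only.* Section 3.3.4.1 keeps him in the trial. Section 6.2.3 requires an end-of-trial visit and does not put it on the day of stopping. Section 6.1 says that the window for the end of trial examination is in the Flow Chart, which is not reproduced in the public text. Immediate closure is not shown for this group, which includes subjects stopped for AEs under Section 3.3.4.1.

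**Would later AEs be lost from the database?** Section 7.3.4 excludes only AEs after the last per-protocol contact. The later questioning is itself required by the protocol, so it can be read as that subject's last such contact. Section 1.2.5 pulls the other way by equating the last contact with the examination. The text is ambiguous, but it does not direct that data be discarded.

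**Day counts** (dosing interval and visit days from Protocol Section 6.2.2):
- Completer, after the first dose: at least 6 days before the next dose.
- Completer, after the second dose: 5 − 1 = 4 days to Day 5, plus the time to the end-of-trial visit.
- Exit in Period 1 on Day 1 or Day 2, examined then, no later contact: 0 to 1 day. Shortfall against the 6-day minimum: 6 − 1 = 5 to 6 − 0 = 6 days.
- Exit on Day 5, same assumptions: 4 days. Shortfall: 6 − 4 = 2 days.
- Stopped just before the second dose: no shortfall.

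**Effect on the tables.** SAP Section 7.8.1 counts subjects with AEs, not events.
- A subject stopped for an on-treatment AE is already in the overall numerator for that treatment. A missed later event changes that count by 0 and can alter only its own preferred-term or category row.
- A subject with no earlier AE who leaves and then has a new, unrecorded event changes the count by 1. With 12 subjects, 1/12 = 8.3 percentage points.
- For scale, Protocol Section 1.2.4.1 reports 16 of 48 treated subjects with any AE in the first-in-man trial, 16/48 = 33.3%. If that rate carried over (an assumption), it would cap the chance of a late first event in such a subject. The expected loss per early leaver without an earlier AE would then be at most 0.333 × 8.3 = 2.8 points.

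**What is still collected.** Sections 5.1.5.2.3 and 6.2.3 follow persisting AEs after the end of trial. Section 5.1.5.2.1 keeps passive reporting of cancer, related SAEs and related AESIs, outside the CRF.

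**The case for a change.** The best argument for a change measures the protocol against its own aim. The sponsor adapted the on-treatment window and the laboratory baseline to the unknown REP, but left the operative sentence in Section 3.3.4 pointing to it. The section plainly wants observation beyond the day of discontinuation, and a sentence or two would supply a determinable end. The clinical part of the first-in-man trial was complete by 14 November 2018, and its data had already led to an amended sampling schedule, so relevant information may have been available.

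Part of this stands. The cross-reference has no value behind it, and the status of an AE first reported at the later questioning is left to interpretation. Section 6.2.3 sets no minimum interval after the dose, so it does not settle the matter by itself.

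The claimed consequences do not stand. Closure on the day of stopping is a possible reading only for subjects who leave the trial. The 5- to 6-day shortfall assumes a very early exit, a same-day examination and no later contact. The 8.3 points further require a new event in a subject with no earlier AE. No discontinuation rate is given that would make this combination likely. A better rule would have to rest on pharmacokinetic data or Flow Chart contacts that are not in the available text, and its length is a clinical matter for the sponsor.

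**Conclusion.** This is an undefined term that a site would fill sensibly, and no change to the plan follows. Sections 3.3.4 and 1.2.5 do not fit together neatly, but the purpose of the later questioning is explicit and its timing is open-ended.

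The effect is confined to descriptive safety tables, for which no hypothesis test is planned, and to the few subjects who may leave early. At the extreme it is one subject in 12, 8.3 percentage points in one treatment column. It is zero in the overall incidence for a subject already counted with an AE. The primary comparison of AUC0-tz and Cmax is unaffected.

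This rests on two assumptions: that sites act on the stated intent and make the later contact where consent allows, and that AEs found then are handled as arising at a per-protocol contact. The Flow Chart could not be read; if it sets a window for the end of trial examination, the point weakens further for subjects who only stop treatment.
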